Following the onset of reaction, patients will be observed for a 3-hour period, during which time no more aspirin doses will be given. TNSS will be recorded at the onset of reaction and again every 30 minutes during this 3-hour period after reaction. Pulmonary function testing is repeated before each dose and at the onset of reaction and if it remains within 85% of their pre-challenge FEV₁, it will be repeated every 90 minutes during the 3-hour period after reaction. If the FEV₁ falls by 15% or more from their morning FEV₁, they will be treated with albuterol, administered by metered dose inhaler (MDI), (up to 8 puffs per administration), and FEV₁ will be repeated every 30 minutes until it has returned to within 85% of their morning pre-challenge FEV₁. If after 3 rounds of albuterol administered by MDI (a total of 24 puffs), the subject's FEV₁ has not returned to within 85% of their morning pre-challenge FEV₁, nebulized albuterol will be administered. No medications (except albuterol and ipratropium) will be used for relief of symptoms during the desensitization until the 3-hour period of observation following onset of reaction is completed, unless required for a patient's safety. A blood sample will be collected 1 hour after the onset of reaction for CBC/differential, platelet activation assays, and platelet-leukocyte aggregate measurements. Urine and nasal samples will be collected at the onset of reaction, and again 90 minutes and 3 hours after the onset of reaction, or if there is no clinical reaction at all, will be collected 90 minutes after the 325mg dose of aspirin is given.

Upon completion of the 3-hour period of observation, further aspirin doses will be administered every 90 minutes until a state of clinical desensitization to and tolerance of 325 mg of aspirin is achieved. Patients will be discharged home 90 minutes after ingestion of 325 mg of aspirin and will be instructed to begin taking daily aspirin, as is part of our standard-of-care for these patients. If required due to time constraints, this visit could proceed onto the next day, during which the subject would begin by repeating the aspirin dose they ended with the day before. However, 95% of our aspirin desensitization procedures done as part of clinical patient care are completed within the first day.

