Upon completion of the 3-hour period of observation, the subject will receive the provocative dose for a second time followed by the next subsequent aspirin dose after 90 minute observation intervals. Once the subject has effectively tolerated, as determined by a study physician, the repeat provocative dose and one subsequent dose bringing the cumulative dose of aspirin ingested during the procedure to ≥ 325 mg, the subject will be discharged home 90 minutes after the last dose, and will be instructed to begin taking daily aspirin, 325mg twice daily for a week until the Phone Call 3, as is part of our standard-of-care for these patients.

Following the 3-hour period of observation, the rescue medications described in Section 7.4 may be used for patient comfort. A sufficient 2-week supply of aspirin will be provided for patients so that they have enough to have them continue daily aspirin through the 2-week follow-up phase.

Follow-up Phase (2 weeks): During the follow-up phase, safety will be assessed through a telephone interview (Phone Call 3) 1 week after **Visit 2** to recommend the patient increases their daily aspirin dose from 325mg twice daily to 650mg twice daily, and again through a telephone interview (Phone Call 4) 1 week after that dose increase to ensure that the patient is tolerating the 650mg twice daily aspirin therapy and to ensure that the patient has an appropriate follow-up visit scheduled with their primary provider within 2 months of initiating the daily aspirin therapy. In order to ensure patient safety and consistency, patients will be prescribed sufficient montelukast at the Screening Visit to have them continue daily montelukast through this follow-up phase.

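### Sections 3.1 and 8.3 set different discharge rules for Visit 2, and under 8.3 a participant who reacts at 81 mg may take the first 325 mg dose at home

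*Combined protocol and SAP*

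**What the plan says.** The Visit 2 ladder is 40.5, 81, 162 and 325 mg, 90 minutes apart (Sections 3.1 and 8.3). After a reaction, dosing stops for a 3-hour observation period. The two sections then diverge.

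- **Section 3.1.** Further doses follow every 90 minutes "until a state of clinical desensitization to and tolerance of 325 mg of aspirin is achieved". On leaving: "Patients will be discharged home 90 minutes after ingestion of 325 mg of aspirin". A spill-over is allowed: "If required due to time constraints, this visit could proceed onto the next day".
- **Section 8.3.** The provocative dose is given again, followed by the next step. The condition for leaving begins "Once the subject has effectively tolerated, as determined by a study physician" and covers "the repeat provocative dose and one subsequent dose bringing the cumulative dose of aspirin ingested during the procedure to" at least 325 mg; then "the subject will be discharged home 90 minutes after the last dose". The participant "will be instructed to begin taking daily aspirin, 325mg twice daily for a week until the Phone Call 3". At that call, one week after Visit 2, the plan is "to recommend the patient increases their daily aspirin dose from 325mg twice daily to 650mg twice daily".

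Section 8.3 also provides for a participant who has no reaction at all: the urine and nasal samples are then taken 90 minutes after the 325 mg step. Section 5.4 says that reactions occur most often at 81 mg or below, and gives no share for each dose.

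**The concern.** One section ties discharge to a 325 mg dose, the other to a 325 mg running total. A participant can reach the total without taking the dose. If that happens, the first 325 mg dose moves from the research centre to the home, with the next scheduled contact a phone call a week later. At the centre, Section 5.4 provides spirometry before each dose, regular vital signs, adrenalin, oxygen and physicians skilled in resuscitation.

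There is also a compliance problem. Section 14.1 permits no deviations and counts any departure from study procedures as one. Where the rules part, discharge that satisfies 8.3 departs from 3.1, and staff and monitors have no text telling them which applies.

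**Working it through.** **Inputs.** Ladder 40.5, 81, 162, 325 mg at 90-minute steps (Sections 3.1 and 8.3); 3-hour observation after onset (both); provocative dose repeated and cumulative threshold of 325 mg (8.3); tolerance of 325 mg (3.1).

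**Formula.** Cumulative dose = ladder doses up to and including the provocative dose + the repeated provocative dose + later steps.

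| Reaction at | Doses under 8.3 | Cumulative | Largest single dose | 8.3 as worded |
|---|---|---|---|---|
| 40.5 mg, one further step | 40.5 + 40.5 + 81 | 162 mg | 81 mg | total not reached |
| 40.5 mg, two further steps | previous + 162 | 324 mg | 162 mg | 1 mg short, and already more than one step |
| 40.5 mg, three further steps | previous + 325 | 649 mg | 325 mg | total reached, but three steps |
| 81 mg | 40.5 + 81 + 81 + 162 | 364.5 mg | 162 mg | met |
| 162 mg | 40.5 + 81 + 162 + 162 + 325 | 770.5 mg | 325 mg | met |
| 325 mg | 40.5 + 81 + 162 + 325 + 325 | 933.5 mg | 325 mg | no higher step exists |
| No reaction | 40.5 + 81 + 162 + 325 | 608.5 mg | 325 mg | no provocative dose to repeat |

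**The 81 mg row under 3.1.** The largest dose is 325 mg. The total is 364.5 + 325 = 689.5 mg if 81 mg is repeated, or 40.5 + 81 + 162 + 325 = 608.5 mg if it is not. Under 8.3, the first 325 mg dose at home is 325/162 = 2.0 times the largest dose observed. Each ladder step is likewise about a doubling.

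**The 40.5 mg rows.** The outcome depends on how staff resolve a rule that cannot be met as written. If the threshold is enforced to the milligram, the 325 mg step is given under observation. If 324 mg is treated as 325 mg, these participants also leave after a largest dose of 162 mg.

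**Sensitivity.** Section 6.1.3.2 describes the first dose as 40 mg. The 81 mg reactor then reaches 40 + 81 + 81 + 162 = 364 mg, and the finding is unchanged.

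**Time for an 81 mg reactor, from the first aspirin dose,** with onset 0 to 90 minutes after the 81 mg dose:
- 8.3: 90 + (0 to 90) + 180 + 90 + 90 = 450 to 540 minutes, or 7.5 to 9.0 hours.
- With the 325 mg step added: 540 to 630 minutes, or 9.0 to 10.5 hours.

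**Endpoints.** PD2 uses symptom scores up to the end of the 3-hour observation. Reaction samples are taken from onset to 3 hours after it. Both precede the doses on which the sections differ. A participant who does not react climbs the whole ladder under either rule.

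**The case against.** The best defence is that 3.1 is the design overview and 8.3 the operative procedure. Section 3.1 does not use the word single, so the cumulative threshold in 8.3 could be how tolerance of 325 mg is put into practice. This is strained: 3.1 itself uses 325 mg as a step on the ladder, and only 8.3 speaks of a cumulative dose. Even if it were intended, 3.1 would need to say so.

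Physician judgment does not close the gap, because it concerns tolerance of the doses given, not of 325 mg.

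The defence is stronger on weight. A reader might infer that the home dose is dangerous. The documents do not support that. By discharge an 81 mg reactor has tolerated a repeat 81 mg and a 162 mg dose in a physician's judgment, has been watched for 90 minutes after the second, and is on montelukast. The plan sends everyone through a later doubling at home, from 325 mg to 650 mg per dose. Section 12.2.1 extends the aspirin adverse-event window to 14 days after completion, and the schedule of events has adverse-event assessment at both follow-up calls. Whether a supervised 325 mg dose is clinically necessary cannot be settled from these documents.

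Three other inferences should be resisted:
- That most participants are affected. The statement in Section 5.4 covers 40.5 mg and 81 mg reactors together.
- That only 81 mg reactors can be affected. That assumes the threshold is enforced exactly for 40.5 mg reactors.
- That 3.1 conflicts with 8.3 by not mentioning the repeat of the provocative dose. Section 8.3 simply adds detail there.

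**Conclusion.** The point holds as a minor safety and consistency issue. The two discharge rules give different results for a reaction at 81 mg: 364.5 mg cumulative and a largest observed dose of 162 mg under 8.3, against an observed 325 mg dose under 3.1. Section 8.3 is also unworkable as worded for reactions at 40.5 mg and 325 mg and for participants who do not react. Of these, only 40.5 mg reactors could also leave without an observed 325 mg dose, and only if 324 mg is accepted as 325 mg.

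The conclusion rests on reading 325 mg in 3.1 as the ladder dose, which is the natural reading. The number of participants affected is unknown. The documents show no harm from the home step, and PD2, the other reaction endpoints and power are unaffected.

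**What to change.** Put one discharge rule in both sections by amending 8.3 to match 3.1. After the 3-hour observation, repeat the provocative dose, continue up the ladder every 90 minutes until a single 325 mg dose is tolerated, and discharge 90 minutes later. State that a participant who reacts at 325 mg need only tolerate the repeat of that dose, and that one who does not react leaves 90 minutes after the 325 mg step. This rule can be met in every case and matches the take-home dose.

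The cost is a wording amendment and, relative to 8.3, one more dose and about 90 minutes for 81 mg reactors. The same would apply to any 40.5 mg reactor who would otherwise have left at 324 mg. Some visits may run into a second day, which 3.1 already allows; it would start by repeating the previous day's last dose.

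If the sponsor intends the cumulative rule, the alternative is to correct 3.1 and reword 8.3 for the 40.5 mg, 325 mg and no-reaction cases. That removes the contradiction but leaves the first 325 mg dose at home for 81 mg reactors.

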8.4. Visit Windows

Study visits should take place within the time limits specified below: the designated visit windows (*i.e. +/- n days*) for each scheduled visit are also indicated on the Table of Events.

Table 3. Table of Events.

Screening Visit	Phone Call 1	Visit 1**	Phone Call 2	Visit 2	Follow-up: Phone Call 3	Follow-up: Phone Call 4
Week 0	Week 1 (± 3 days)	Week 2 (± 5 days)*	Week 3 (± 3 days)	Week 6 (+10 days/- 5 days)	Week 7 (± 3 days)	Week 8 (± 3 days)

*The run in period after the Screening Visit can be skipped for Visit 1 if the subject is already taking montelukast at the time of the Screening Visit, so that for patients already taking montelukast for at least 2 weeks prior to Screening, Visit 1 could occur as soon as 24 hours after Screening.

**A 6-week supply of ifetroban will be provided at Visit 1.

9. Mechanistic Assays

Assess the effect of TP receptor blockade in vivo on platelet activation in vivo. 20-40 μ L of blood or platelet-rich plasma will be stained with Abs against CD61 and P-selectin. The percentages of P-selectin⁺ events in the CD61⁺ platelet-sized

gate will be determined. The changes in P-selectin⁺ platelets will be correlated with the corresponding changes in urinary eicosanoids and nasal lavage eicosanoids.

Assess the effect of TP receptor blockade on platelet activation in vitro. Platelet rich plasma obtained at visit 1 and before the challenge at Visit 2 will be stimulated with LTC₄ or with U46619 for 30 min. Platelets will be monitored for activation, and platelet-free supernatants monitored for TXA₂ generation.

Determine the effect of TP receptor blockade on release of mediators derived from cell activation. Nasal lavage fluids will be collected once at Visit 1 and again prior to administration of aspirin at Visit 2 and then serially at Visit 2 during the reactions to aspirin, and will be monitored by ELISA for mediators derived from mast cell and platelet activation.

Monitor innate Type 2 cytokine expression. RNA from nasal scrapings obtained at Visits 1 and 2 (before challenge) will be subjected to qPCR analysis for expressions of IL-33 and TSLP. Nasal fluid IL-33 levels will be measured at baseline and during reactions.

Monitor activation of mast cells and their associated eicosanoids. Total tryptase concentrations in nasal fluid and plasma/serum will be measured by ELISA (performed at Virginia Commonwealth University on a fee-for service basis). Urinary PG metabolites will be measured by GC-MS and LTE₄ by LC-MS as in our previous studies,¹² and nasal eicosanoids will be measured by ELISA.

10. Biospecimen Storage

The following biospecimen types will be obtained with the intention to be analyzed within the context of this protocol, but in some cases, there may be excess sample volume left over after the specified analyses. In those cases, the excess volume would be stored in our long-term biorepository (Core C) as detailed in the AADCRC overall proposal.

- Nasal fluid
- Nasal cells
- Urine
- Plasma
- Serum

Sample storage data will be accessible only to members of the AADCRC projects at BWH, and the BWH Asthma Research Center via clinical sample management software. Before patient visits, anticipated samples will be entered into the database and associated with the patient ID and the date and number of the visit so that labels for sample containers can be printed and applied. When samples are received, the entries will be updated to reflect the actual type and number of samples obtained, any aliquots of samples to be made for storage purposes will be accounted for, labels will be printed for the aliquot tubes, and space in a dedicated -80°C freezer will be assigned. This process will permit tracking of the history of all samples, as well as multi-parameter searches to identify and locate samples with the characteristics and thus minimize temperature fluctuations in the freezer when samples are sought.

11. Criteria for Participant and Study Completion and Premature Study Termination

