suspected AERD will be enrolled in this study with the anticipation that there will be a dropout rate of 10-20%. All subjects will have a clinical history consistent with AERD (asthma, nasal polyposis, and a history of a suspected reaction to a nonselective COX inhibitor). All subjects will be on standard therapy for persistent asthma, which may include some combination of inhaled glucocorticoids, oral glucocorticoids, long- and short-acting β -agonists, and CysLT₁R antagonists. We will exclude individuals being treated with omalizumab (monoclonal anti-IgE) or mepolizumab (monoclonal anti-IL-5), as the effects of these medications on the aspirin-induced reactions in AERD are not known. Detailed Inclusion and Exclusion criteria are listed in Section 4.2 and 4.3. We have found that all of the subjects who are currently enrolled in our trial of prasugrel and meet these strict inclusion criteria exhibited respiratory reactions to aspirin, confirming their diagnosis of AERD. The Study Schema overview is shown in **Figure 3**.

At a Screening Visit for patients with AERD, the study will be explained, and the participant will sign informed consent before undergoing any procedures. A physical exam, baseline ECG, spirometry and lab work (CBC, urine pregnancy) will be performed. Assessments of asthma control (ACQ score, which evaluates asthma control over the preceding 1 week), and nasal symptoms (SNOT-22 score, which assesses symptoms over the preceding 2 weeks) will also be obtained.

There will be a 2-week Run-In after the Screening Visit during which subjects will begin taking montelukast 10mg daily (if not already on montelukast as part of their regular asthma care) and will stop taking zileuton (if they are on

zileuton as part of their regular asthma care). A telephone encounter (**Phone Call 1**) 1 week later will ensure safety and confirm stable asthma.

After the 2-week Run-In Period on montelukast, subjects will come into the ARC for **Visit 1**. Interval history, physical exam, ACQ, SNOT-22, pre-challenge TNSS and spirometry will be recorded, along with FeNO. Blood will be drawn for CBC/differential, and cellular profiling and activation assays. A urine sample will be collected for pregnancy and eicosanoid metabolites. Nasal lavage for cytokine and eicosanoid measurements and a nasal epithelial scraping sample for RNA extraction will be taken. Subjects will be randomized to receive ifetroban (200 mg dose per day), or placebo for 4 weeks.

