7.3. Prohibited Medications

- **Zileuton.** Subjects who were previously taking zileuton will discontinue it at the Screening Visit so as not to interfere with cysLT production and the accurate assessment of clinical symptoms occurring during the aspirin desensitization. A telephone encounter (**Phone Call 1**) 1 week after the Screening Visit will ensure safety and confirm stable asthma for those patients who were asked to discontinue zileuton. Zileuton may be used as a rescue medication during the aspirin desensitization procedure, but the subject must be free of zileuton for at least 3 weeks preceding each Study Visit.
- **Anticoagulants.** Use of warfarin or any other antiplatelet or anticoagulant medications will be prohibited.
- **Beta-blockers.** Due to the risk of bronchospasm associated with beta blockers, current use of any oral beta blocker will be prohibited.
- **NSAIDs.** The use of any additional non-steroidal anti-inflammatory drugs (NSAIDs), except the aspirin dosing as detailed for the study, will be prohibited throughout their participation in the study.
- **Biologics.** The use of any biologics is prohibited in the 120 days prior to Visit 1, and throughout the study.

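### A subject who stops zileuton at Screening, as told, cannot meet the 3-week zileuton-free rule at any Visit 1 that Table 3 allows, and may be randomized before Phone Call 1

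*Combined protocol and SAP*

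**What the plan says.** Section 7.3 (Prohibited Medications) gives two instructions in one bullet. The first is "Subjects who were previously taking zileuton will discontinue it at the Screening Visit". The second is that "the subject must be free of zileuton for at least 3 weeks preceding each Study Visit". The same bullet places Phone Call 1 one week after Screening, a call that "will ensure safety and confirm stable asthma for those patients who were asked to discontinue zileuton". Section 3.1 repeats the stop: at the start of a 2-week run-in, subjects begin montelukast if they are not already on it "and will stop taking zileuton (if they are on" it for their usual care.

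Section 8.3 (Study Visits) describes Visit 1 and Visit 2, calls Visit 1 the baseline visit, and places randomization there. Table 3 in section 8.4 sets Phone Call 1 at Week 1 ± 3 days, Visit 1 at Week 2 ± 5 days, and Visit 2 at Week 6 (+10/−5 days). A footnote waives the run-in "for patients already taking montelukast for at least 2 weeks prior to Screening": for them, "Visit 1 could occur as soon as 24 hours after Screening". The footnote does not mention zileuton.

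Exclusion 3 in section 4.3, and the matching item in the synopsis, bar current zileuton use.

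**The concern.** Three rules meet at Visit 1: when zileuton stops, how long the subject must be off it, and when the visit takes place. For a subject who stops at Screening they cannot all be obeyed. Section 14.1 permits no deviations, so site staff who follow the stop instruction must breach either the washout or the visit window. Exclusion 3 adds a third possibility, that the subject was never eligible.

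Visit 1 is the reference for the secondary changes in FEV1, ACQ, SNOT-22, FeNO, eicosanoids and other mediators (section 3.3). If zileuton is still acting at Visit 1 and is gone by Visit 2, that subject's change mixes zileuton withdrawal with four weeks of study treatment. The questionnaires look back as well. Section 3.1 describes the "SNOT-22 score, which assesses symptoms over the preceding 2 weeks" and the "ACQ score, which evaluates asthma control over the preceding 1 week", so at an early Visit 1 part of the recall period can fall on zileuton.

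There is also a question of order. The footnote depends on montelukast alone, so a subject on both drugs could stop zileuton one day and be randomized the next, before the call that is meant to check asthma stability off zileuton.

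**Working it through.** **Inputs.** Screening is day 0 and is taken as the last zileuton day (sections 3.1 and 7.3). Weeks are counted as multiples of 7 days from Screening. Windows and the 24-hour footnote are from Table 3, the washout of 3 × 7 = 21 days from section 7.3, and recall periods of 14 days (SNOT-22) and 7 days (ACQ) from section 3.1.

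**Step 1: windows in days after Screening.**
- Phone Call 1: 7 ± 3 = days 4 to 10.
- Visit 1: 14 ± 5 = days 9 to 19; day 1 under the footnote.
- Visit 2: 42 − 5 to 42 + 10 = days 37 to 52.

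**Step 2: washout and recall at Visit 1 on day d.** The shortfall is 21 − d. Recall days before the stop are max(0, 14 − d) for SNOT-22 and max(0, 7 − d) for ACQ.

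| Visit 1 | d | Days short of 21 | SNOT-22 recall days before the stop | ACQ recall days before the stop |
|---|---|---|---|---|
| Footnote minimum | 1 | 20 | 13 of 14 | 6 of 7 |
| Window opens | 9 | 12 | 5 of 14 | 0 of 7 |
| Nominal | 14 | 7 | 0 of 14 | 0 of 7 |
| Window closes | 19 | 2 | 0 of 14 | 0 of 7 |

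The first compliant day is 21, which is 2 days after the window closes. No permitted Visit 1 satisfies the rule.

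**Step 3: order of Phone Call 1 and randomization.** A day-1 Visit 1 comes 3 to 9 days before the call window (4 − 1 = 3; 10 − 1 = 9). Even in the standard windows, a Visit 1 on day 9 can precede a call on day 10.

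**Step 4: Visit 2.** Counted from Screening, its earliest day is 37. Counted from a day-1 Visit 1, with four weeks of treatment and the 5-day allowance, it is 1 + 28 − 5 = day 24. Both are at least 21, so the rule is met at Visit 2.

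**Step 5: effect on a change score.** Suppose withdrawal adds an average amount w to a user's change, and users make up fractions p and q of the ifetroban and placebo arms. The difference between arms then shifts by (p − q) × w. Under randomization p − q has expectation zero, so the expected treatment effect does not move. Variance rises, and any one trial can have p ≠ q by chance. The documents give none of p, q or w.

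**The case against.** The strongest reply is that the affected group may be empty. If exclusion 3 is applied at Screening, where eligibility is verified, no zileuton user enters. That is a possible reading, but sections 3.1 and 7.3 tell users to stop and carry on, and these instructions would be pointless if such users were barred. The text supports both readings, and the number of users is not given.

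A second reply is that section 7.3 stops zileuton to protect cysLT production and symptom assessment during the desensitization, which takes place at Visit 2, where the washout is met. This stands for the purpose of the stop. The 3-week sentence nevertheless covers each Study Visit, and Visit 1 is one of the two.

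A third is that the footnote only permits an early visit and cannot override a separate obligation. Read that way, a zileuton user could not use it. But the standard window fails too, and nothing in the footnote warns the site.

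On safety, Visit 1 includes interval history, examination, ACQ and spirometry, Phone Call 2 repeats an asthma check one week into treatment, and the footnote does not cancel Phone Call 1. Monitoring is not lost; what can go wrong is that the call falls after randomization.

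A reader might infer three stronger things. One is that the primary result is compromised; Step 4 rules this out. Another is that the secondary treatment effects are biased or diluted. Withdrawal shifts a user's change in either arm, so random allocation leaves the expected difference where it was, and nothing in the documents points to ifetroban acting differently in recent zileuton users. The third is a definite error in urinary LTE4. Section 13.4.4 calls a 30% fall roughly half of zileuton's effect, which suggests a full effect of 2 × 30% × 0.37 = 0.22 ng/mg Cr against the 0.14 sought. But 0.14/0.37 is 38%, not 30%, and both the number of users and the speed of recovery after stopping are unknown. Any between-arm figure would rest on assumed inputs, and it is zero if users are balanced or recovery is complete by Visit 1.

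**Conclusion.** The inconsistency is real and follows from the calendar alone: a subject who stops zileuton at Screening is 2 to 12 days short of the required washout anywhere in the standard Visit 1 window, and 20 days short at the footnote minimum. Such a subject may also be randomized before Phone Call 1. Exclusion 3 is a third conflicting rule, not the answer.

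The consequence is limited. PD2 and the aspirin-reaction endpoints at Visit 2 stand, because Visit 2 falls at least about 24 days after the stop. What remains is added noise and possible chance imbalance in the changes from Visit 1 (eicosanoids, FEV1, ACQ, SNOT-22, FeNO), from an unknown and probably small number of subjects. Its size cannot be computed from the documents. The conclusion assumes that the stop takes place at Screening and that weeks are counted from that day; a subject who had already stopped long enough before Screening would comply. The correction is worth making because eligibility, washout and visit timing cannot be followed together as written, whatever the size of the effect.

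**What to change.** **Preferred.** Exclude anyone who took zileuton within 3 weeks before Visit 1, reword exclusion 3 (and its synopsis counterpart) to say so, and delete the stop-at-Screening text in sections 3.1 and 7.3.

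**Alternative.** Keep the stop at Screening and reword exclusion 3 to allow it. For these subjects, set Visit 1 at least 21 days after the last zileuton dose, with Phone Call 1 completed first. Phone Call 2, Visit 2 and the later calls must then be counted from Visit 1. Counted from Screening, a Visit 1 on day 21 puts Phone Call 2 at 21 + 7 = day 28, outside its current 21 ± 3 = days 18 to 24. Any Visit 1 after day 24 puts the end of four weeks of treatment past 24 + 28 = day 52, the last permitted day for Visit 2.

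**Either way.** Limit the Table 3 footnote to subjects on montelukast for at least 2 weeks and off zileuton for at least 3 weeks.

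**Cost.** Both options are wording changes with no added visits. The preferred option loses a few zileuton users from recruitment. The alternative keeps them, but they wait about one week longer than the nominal run-in (21 − 14 = 7 days) or slightly more, with montelukast supply to match. Those who would otherwise have used the footnote lose that shortcut.
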